16.5 Electrocardiogram (ECG)

ECGs will be measured at screening Visit 1, Visit 3, Visit 6, and Visit 8/EOT, and graded as normal or abnormal. Abnormal findings or changes from baseline will be further classified as not clinically significant (NCS) or clinically significant (CS). In the event abnormal ECG results requires additional follow up, ECGs may be performed at unscheduled visits or at a study visit that an ECG is not required per protocol. ECG data performed outside of the protocol specified time points will be captured in the EDC on an "Unscheduled Visit" eCRF and mapped to the nearest scheduled visit as defined in [Section 9.3](#). ECG grades and shift from baseline will be summarized with counts and percentages for each visit for the Safety set. All clinically significant findings will be recorded as AEs in the eCRF and followed until resolution. Once resolved, the AE eCRF page(s) will be updated. A subject listing of the ECG results will also be produced.

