### 7.2.1.2.7 Adverse Events of Special Interest

The following are considered adverse events of special interest (AESI):

- Hepatic injury defined by the following alterations of liver parameters:  
For subjects with normal liver function at baseline an elevation of AST and/or ALT  $\geq$  3-fold ULN combined with an elevation of total bilirubin  $\geq$  2-fold upper limit of normal (ULN) measured in the same blood draw sample. Subjects showing these lab abnormalities need to be followed up according to [Section 17.1.2](#).
- Abrupt decrease ( $>$  15 letters lost from baseline) of BCVA
- QTc prolongation ( $>$  +50 ms from baseline and  $>$  450 ms)

Protocol-specific AESIs are to be reported in an expedited manner similar to SAEs even if they do not meet any of the criteria for an SAE (see [Section 7.2.1.2.2](#)).

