 - For subjects with normal liver function at baseline an elevation of aspartate aminotransferase (AST) and/or alanine aminotransferase (ALT) ≥ 3 -fold the upper limit of normal (ULN) combined with an elevation of total bilirubin ≥ 2 -fold the ULN measured in the same blood draw sample;
- Abrupt decrease of BCVA (> 15 letters lost from baseline);
- QTc interval prolongation ($> +50$ ms from baseline and > 450 ms).

An overall tabular summary of TEAEs will be presented that includes the number and percentage of subjects who experienced at least one TEAE. These summaries will also include breakdowns of TEAEs further categorized as ocular or non-ocular, and within these categories as drug-related TEAEs, TEAEs with CTCAE Grade 3/4/5, drug-related TEAEs with CTCAE Grade 3/4/5, TEAEs with an outcome of death, serious TEAEs, drug-related serious TEAEs, TEAEs leading to discontinuation of IMP and drug-related TEAEs leading to discontinuation of IMP.

Furthermore, the number and percentage of subjects with TEAEs by SOC and PT; by SOC, PT and maximal severity; by SOC and PT for TEAEs; by SOC and PT for SAEs; and by SOC and PT for TEAEs leading to subject withdrawal will be presented. Separate summaries will be provided for ocular and non-ocular TEAEs (including systemic). Adverse events of special interest will also be summarized by SOC and PT. These summaries by SOC and PT will be at the subject level. If a subject reports the same PT multiple times within the same SOC, that PT will only be counted once within that SOC. As with the PT, if a subject reports multiple conditions within the same SOC, that SOC will only be counted once.

All AEs (including non-TEAEs) will also be presented in subject listings.

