14.2.7.2	Presence of Leakage from Choroidal Neovascularization as Demonstrated by Fluorescein Angiography in the Study Eye at Scheduled Visits	PP Set
14.2.7.3	Summary of Size of Leakage from Choroidal Neovascularization (Number of Disc Areas) and Change from Baseline as Demonstrated by Fluorescein Angiography in the Study Eye at Scheduled Visits	Evaluable Set
14.2.7.4	Summary of Size of Leakage from Choroidal Neovascularization (Number of Disc Areas) and Change from Baseline as Demonstrated by Fluorescein Angiography in the Study Eye at Scheduled Visits	PP Set
Safety Analyses		
14.3.1.1	Overall Summary of Treatment-Emergent Adverse Events	Safety Set
14.3.2.1	Summary of All Ocular Treatment-Emergent Adverse Events by System Organ Class and Preferred Term	Safety Set
14.3.2.2	Summary of All Non-Ocular Treatment-Emergent Adverse Events by System Organ Class and Preferred Term	Safety Set

Table Number	Title	Set
14.3.3.1	Summary of All Ocular Treatment-Emergent Adverse Events Suspected to be Related to Investigational Medicinal Product by System Organ Class and Preferred Term	Safety Set
14.3.3.2	Summary of All Non-Ocular Treatment-Emergent Adverse Events Suspected to be Related to Investigational Medicinal Product by System Organ Class and Preferred Term	Safety Set
14.3.4.1	Summary of All Ocular Serious Treatment-Emergent Adverse Events by System Organ Class and Preferred Term	Safety Set
14.3.4.2	Summary of All Non-Ocular Serious Treatment-Emergent Adverse Events by System Organ Class and Preferred Term	Safety Set
14.3.5	Summary of All Adverse Events of Special Interest by System Organ Class and Preferred Term	Safety Set
14.3.6.1	Summary of All Ocular Treatment-Emergent Adverse Events Leading to Subject Withdrawal by System Organ Class and Preferred Term	Safety Set
14.3.6.2	Summary of All Non-Ocular Treatment-Emergent Adverse Events Leading to Subject Withdrawal by System Organ Class and Preferred Term	Safety Set
14.3.7.1	Summary of Ocular Treatment-Emergent Adverse Events by Maximum Severity, System Organ Class and Preferred Term	Safety Set
14.3.7.2	Summary of Non-Ocular Treatment-Emergent Adverse Events by Maximum Severity, System Organ Class and Preferred Term	Safety Set
14.3.8.1	Summary of Slit Lamp Biomicroscopy	Safety Set
14.3.8.2.1	Shift in Overall Results of Slit Lamp Biomicroscopy	Safety Set
14.3.8.2.2	Shift in Slit Lamp Biomicroscopy Anterior and Vitreous Chamber	Safety Set

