14.3.8.2.3	Shift in Slit Lamp Biomicroscopy Hypopyon and Retinal Tear and Detachment	Safety Set
14.3.8.2.4	Shift in Slit Lamp Biomicroscopy Lens Status	Safety Set
14.3.8.2.5	Shift in Slit Lamp Biomicroscopy Lens Opacity for Phakic Eyes	Safety Set
14.3.9	Summary of Intraocular Pressure	Safety Set
14.3.10.1.1	Summary of Clinical Laboratory Values - Biochemistry	Safety Set
14.3.10.1.2	Shift in Clinical Laboratory Values - Biochemistry	Safety Set
14.3.10.2.1	Summary of Clinical Laboratory Values - Coagulation	Safety Set
14.3.10.2.2	Shift in Clinical Laboratory Values - Coagulation	Safety Set
14.3.10.3.1	Summary of Clinical Laboratory Values - Hematology	Safety Set
14.3.10.3.2	Shift in Clinical Laboratory Values - Hematology	Safety Set
14.3.11	Summary of Vital Signs	Safety Set
14.3.12.1	Summary of Electrocardiogram Overall Results	Safety Set
14.3.12.2	Shift in Electrocardiogram Overall Results	Safety Set

25. Listings

Listing Number	Title	Set
16.2.1	Subject Disposition	ITT Set
16.2.2	Protocol Deviations	ITT Set

Listing Number	Title	Set
16.2.3.1	Inclusion and Exclusion Criteria	All Patients
16.2.3.2	Subjects Excluded from Analysis Sets	ITT Set
16.2.3.3	Informed Consent	ITT Set
16.2.4.1	Demographics	ITT Set
16.2.4.2	Ocular Medical History	ITT Set
16.2.4.3	Non-Ocular Medical History	ITT Set
16.2.4.4	Prior and Concomitant Ocular Medications	ITT Set
16.2.4.5	Prior and Concomitant Non-Ocular Medications	ITT Set
16.2.4.6	Prior Anti-VEGF IVT Treatment	ITT Set
16.2.5.1	Study Drug Administration	ITT Set
16.2.6.1	Best Corrected Visual Acuity Scores (ETDRS)	ITT Set
16.2.6.2	Spectral Domain – Optical Coherence Tomography	ITT Set
16.2.6.3	Fundus Photography	ITT Set
16.2.6.4	Fluorescein Angiography	ITT Set
16.2.7.1	All Adverse Events	ITT Set
16.2.7.2	Serious Adverse Events	ITT Set
16.2.7.3	Adverse Events of Special Interest	ITT Set
16.2.7.4	Adverse Events Leading to Subject Withdrawal	ITT Set
16.2.7.5	Deaths	ITT Set
16.2.8.1	Slit-Lamp Biomicroscopy	ITT Set
16.2.8.2	Intraocular Pressure	ITT Set
16.2.8.3	Vital Signs	ITT Set
16.2.8.4	Physical Examination	ITT Set
16.2.8.5	Biochemistry	ITT Set
16.2.8.6	Hematology	ITT Set
16.2.8.7	Coagulation	ITT Set
16.2.8.8	Urine Analysis	ITT Set
16.2.8.9	Serology	ITT Set
16.2.8.10	Electrocardiogram	ITT Set

26. Figures

Figures that will be included in the topline delivery are shown in boldface font.

Figure Number	Title	Set
14.2.1	By-Visit Box Plot Summary of BCVA Letter Score in the Study Eye	Evaluable Set

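### The SAP counts adverse events of special interest only as reported terms and never applies their numeric definitions to the recorded data; the gap is largest for QTc

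*SAP*

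**What the plan says.** **Definition.** Protocol 7.2.1.2.7 sets the QTc event at a rise of more than "50 ms from baseline and" a value above 450 ms. SAP 16.1 lists "QTc interval prolongation" with the same two-part limit ("ms from baseline and > 450 ms"). The other two AESIs are also numeric. One is a loss of more than 15 BCVA letters from baseline. The other, for subjects with normal liver function at baseline, is AST and/or ALT at least 3 times the upper limit of normal (ULN) with total bilirubin at least 2 times ULN in the same blood draw.

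**ECG analysis.** Under SAP 16.5, ECGs are "graded as normal or abnormal", and abnormal findings or changes are then classed as clinically significant or not. The planned output is: "ECG grades and shift from baseline will be summarized with counts and percentages for each visit for the Safety set". The ECG tables in SAP Section 24 are 14.3.12.1, "Summary of Electrocardiogram Overall Results", and the matching shift table 14.3.12.2. Listing 16.2.8.10 covers ECGs, but its contents are not specified.

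**AESI analysis.** The table is 14.3.5, "Summary of All Adverse Events of Special Interest by System Organ Class and Preferred Term", on the Safety Set. Listing 16.2.7.3 gives the individual events.

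**Reporting duty.** Protocol 7.2.1.2.7 requires expedited reporting of AESIs even when they are not serious, and Protocol 7.2.1.3 sets the deadline.

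**The concern.** The documents single out three events by objective limits on data that the trial collects, and then count them only through the AE form. System organ class and preferred term are codes given to reported events, so Table 14.3.5 can show only what a site recognised and filed. For QTc, recognition means subtracting the screening value from each later reading.

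At stake is how well the AESI count is supported. Safety is the only secondary endpoint, and there is no control arm. A reported count of zero would be read as showing that no subject met the definition. As planned, it shows only that no investigator reported one.

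**Working it through.** The documents give no figure on this point to reproduce. The check follows each AESI from recorded value to reported count.

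**1. QTc: can the grade stand in for the definition?** For baseline QTc *b*, the event needs a value above max(450, *b* + 50) ms. Protocol 5.2 excludes a Bazett QTc of 430 ms or more in men and 450 ms or more in women, with confirmation on a repeat ECG. Within that range, in whole milliseconds:

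| Baseline (ms) | AESI if QTc exceeds (ms) |
|---|---|
| 400 or less | 450 |
| 410 | 460 |
| 420 | 470 |
| 429 | 479 |
| 449 | 499 |

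A reading of 455 ms meets the definition from a baseline of 400 (rise 55) but not from 410 (rise 45). An overall grade cannot separate these two subjects. The clinical-significance class is a judgement with no numeric criterion.

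**2. QTc: how does a finding become an AE?** Three rules apply, and they differ:
- Protocol 7.2.3: abnormal ECG findings during the trial are reported as AEs.
- Protocol 7.2.1.2.6: ECG changes are recorded if the investigator judges them clinically relevant.
- SAP 16.5: clinically significant findings are recorded.

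**3. QTc: baseline, formula and unscheduled readings.** The schedule has ECGs at Visits 1, 3, 6 and 8 and none at Visit 2. Under SAP 9.2 the baseline is therefore normally the screening ECG. Bazett is named only in the exclusion criterion, and no correction is stated for the AESI. SAP 16.5 expects unscheduled ECGs after abnormal results, but SAP 9.3 keeps one assessment per visit window in the summary tables, so a qualifying unscheduled reading may not enter them.

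**4. BCVA.** Table 14.2.1.3 counts changes of −15 letters or worse by visit. It differs from the AESI in two ways. It includes a loss of exactly 15, where the AESI needs more than 15. It also uses the Evaluable Set, which Protocol 10.3 limits to subjects with at least 3 weeks of treatment, so an abrupt loss in a subject who stops earlier is left out.

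**5. Liver.** SAP 16.4 summarises biochemistry values and changes, and Table 14.3.10.1.2 gives shifts. None of these flags AST or ALT and bilirubin jointly in one sample.

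**6. Size.** Scheduled post-baseline ECGs number at most 30 × 3 = 90. One subject is 1/30 = 3.3%. The exact one-sided 95% upper bound for 0 of 30 is 1 − 0.05^(1/30) = 9.5%. For 1 of 30 it solves (1 − p)^30 + 30p(1 − p)^29 = 0.05, giving 14.9%.

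The chance of at least one uncounted subject is 1 − [1 − p(1 − s)]^30, for true rate p and reported share s. The documents give neither, so these values are assumptions:

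| Assumed p | s = 1 | s = 0.75 | s = 0.50 | s = 0.25 |
|---|---|---|---|---|
| 5% | 0% | 31% | 53% | 68% |
| 10% | 0% | 53% | 79% | 90% |

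Deriving the event from recorded values corresponds to s = 1 for recorded ECGs.

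**The case against.** The strongest reply is that the protocol already provides a safeguard. The AESI reporting duty does not depend on the clinical-significance class, and Protocol 7.2.3 separately has abnormal ECG findings reported as AEs. A qualifying event is missed only if a site fails in its duty. ECGs stay in the medical record, sites are monitored (Protocol 9), and ECG and AESI listings are planned. With at most 90 scheduled post-baseline ECGs, a manual check may be possible. The safety analysis is descriptive, so neither upper bound above is a planned statement, and both would apply to a missed event of any kind.

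Much of this stands. A reader might infer that qualifying events will vanish, that the count cannot be checked, or that it is biased downward. The documents support none of these. An abnormal ECG judged not clinically significant still appears in the grade and shift tables. The listing may hold QTc values. No reporting rate is given from which to establish a bias. Nor is the gap equal across the three AESIs: BCVA scores are listed for all ITT subjects (16.2.6.1), biochemistry is listed (16.2.8.5), and both have numeric summaries.

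The reply does not supply the missing step. Nothing in the SAP compares reported AESIs with recorded values, and the documents do not confirm that QTc in milliseconds reaches the database or the listing.

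**Conclusion.** The point holds as a gap in the analysis plan. The AESI definitions are numeric, and no planned analysis applies them or checks the reported count against them. The gap is largest for QTc, where no numeric summary is planned. It is smaller for BCVA, where the nearest table uses a slightly different cut-off and leaves out subjects with under 3 weeks of treatment. It is also smaller for liver, where only the joint same-sample flag is missing.

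The documents do not show that any event will be missed, or how many. The 31% to 90% range rests wholly on assumed rates and reporting shares; it illustrates the dependence on reporting and does not measure it. What can be said is that each subject is worth 3.3 percentage points. This is a cheap improvement that makes the AESI count verifiable. It does not threaten the primary analysis.

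The text available for this review lacks SAP Section 8 and the start of Section 9. By their titles these cover analysis sets and general conventions, and they are unlikely to change this reading.

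**What to change.** In SAP 16.1 and 16.5:

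1. Derive all three AESIs in the Safety Set from all recorded post-baseline data, scheduled and unscheduled, rather than from the one assessment per window kept under SAP 9.3.
2. For QTc, name the correction formula and state that baseline is the last pre-dose ECG, normally the screening one.
3. Summarise QTc and its change from baseline by visit, and count subjects who meet the stated AESI limit at any post-baseline ECG.
4. For BCVA, apply the AESI limit itself. For liver, flag the joint criterion within one blood sample, and state how normal liver function at baseline is determined.
5. Show derived beside reported AESI counts, and list every subject on whom the two disagree.

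Separately, reconcile Protocol 7.2.1.2.6, Protocol 7.2.3 and SAP 16.5 on when an ECG finding is recorded as an AE.

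The cost is one or two small tables. If the eCRF holds only the ECG grade, the QTc value must also be entered: at most 30 × 4 = 120 scheduled readings (screening and Visits 3, 6 and 8), plus any unscheduled ones. No visit or procedure is added.

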16.6 Vital Signs

Vital signs (blood pressure, pulse rate and respiration) and temperature will be summarized at all scheduled visits using descriptive statistics for the Safety set. Blood pressure includes systolic blood

pressure (SBP) and diastolic blood pressure (DBP). Change from baseline will also be summarized to each post-baseline visit.

A subject listing of the vital signs results will also be produced.

16.7 Physical Examination

A general physical examination including height (measured only at screening) and weight will be performed at screening Visit 1, Visit 2, Visit 4, Visit 6, Visit 8/EOT and Visit 10/FU.

Physical examination data will be listed to indicate whether the physical examination was conducted or not, but no tabular summaries will be produced.

17. Analysis of the Exploratory Endpoints

17.1 SD-OCT and Fundus Photography/Fluorescein Angiography

SD-OCT will be assessed at all scheduled study visits. The retinal layers and thickness will be visualized and measured by OCT and will be investigated by a trained person using only specified OCT equipment. Reported CST values will be exclusive of the sub-retinal pigment epithelial (RPE) layer fluid.

FP/FA will be conducted on the study eye at Screening (Day -7 to -2; up to 14 days prior to Visit 1 is also acceptable for FP/FA) and Visit 8/EOT (Day 43±1).

The following ophthalmic endpoints described below will be measured in an exploratory manner to investigate the extent, onset, and duration of action. Change from baseline in the study eye of the quantitative endpoints will be analyzed in a manner similar to the primary efficacy endpoint. Qualitative endpoints will be summarized for the study eye using counts and percentages for the Evaluable and PP sets. Subject listings will also be provided for these endpoints and will include collected data for the fellow eye.

- CST (μm) measured by SD-OCT, absolute and change from baseline
 - CST in the study eye will also be summarized for each scheduled visit using box plots.
- Presence and maximum height (microns) of IRF by SD-OCT over time, absolute and change from baseline
- Presence and maximum height (microns) of SRF by SD-OCT over time, absolute and change from baseline
- Presence and maximum height (microns) of PED by SD-OCT over time, absolute and change from baseline
 - Collected in EDC as RPE detachments and maximum height of the detachments are collected when present.

- Maximum height of PED in the study eye will also be summarized for each scheduled visit using box plots.
- Presence and size (number of disc areas) of CNV measured by SD-OCT and FP/FA, absolute and as change from baseline.
- Presence and size (number of disc areas) of CNV leakage as demonstrated by FP/FA, absolute and as change from baseline

The following ophthalmic endpoints will be captured in EDC as part of standard SD-OCT and FP/FA assessments. These endpoints will not be summarized (except for macular volume, which will be summarized for the study eye at scheduled visits using box plots) but will be presented in subject listings.

- Macular Volume (mm³) as measured by SD-OCT
- Presence of Intraretinal Cystoid Spaces as measured by SD-OCT
- Presence of Lesion in the CNV (including size of the lesion) as measured by FP/FA
- Presence of RPE atrophy as measured by FP/FA
- Presence of Hemorrhage in the PED (including area of the hemorrhage) as measured by FP/FA
- Presence of Disciform Scar/Retinal Fibrosis as measured by FP/FA

18. Interim Analyses

Continuous data monitoring will be performed. One interim analysis will be performed when two-thirds of all entered subjects have reached Day 15 (Visit 4). The interim analysis will include only a subset of the secondary endpoint (i.e., accumulated AE information).

Recruitment into the trial will be stopped if the interim analysis shows relevant safety problems with ALK4290. No formal futility analysis will be conducted.

19. Pharmacokinetic Analysis

A separate PK plan will be created to describe details pertinent to the analysis of collected PK data.

20. Biomarker Analysis

A separate biomarker plan will be created to describe details pertinent to the exploratory analysis of collected biomarker data.

21. Changes from Protocol-Stated Analyses

Not applicable.

22. References

Not applicable.

23. Revision History

Documentation of revision to the SAP will commence after approval of the Final version 1.0.

24. Tables

Tables that will be included in the topline delivery are shown in boldface font and the tables, listings, and figures for the interim analyses are italicized.

Table Number	Title	Set
14.1.1	Subject Disposition	All Patients
14.1.2	Demographics and Baseline Characteristics	ITT Set
14.1.3.1	Ocular Medical History	ITT Set
14.1.3.2	Non-Ocular Medical History	ITT Set
14.1.4.1	Ocular Concomitant Medications	ITT Set
14.1.4.2	Non-Ocular Concomitant Medications	ITT Set
14.1.5	Compliance with Study Drug	Safety Set
14.1.6	Exposure to Study Drug	Safety Set
Primary and Exploratory Efficacy Analyses		
14.2.1.1	Summary of Study Eye BCVA Letter Score and Change from Baseline at Scheduled Visits	Evaluable Set
14.2.1.2	Summary of Study Eye BCVA Letter Score and Change from Baseline at Scheduled Visits	PP Set
14.2.1.3	Categorical Summary of Study Eye BCVA Letter Score Change from Baseline at Scheduled Visits	Evaluable Set
14.2.2.1	Summary of Study Eye Central Subfield Thickness (µm) and Change from Baseline as Measured by SD-OCT at Scheduled Visits	Evaluable Set
14.2.2.2	Summary of Study Eye Central Subfield Thickness (µm) and Change from Baseline as Measured by SD-OCT at Scheduled Visits	PP Set
14.2.3.1	Presence of Intraretinal Fluid as Measured by SD-OCT in the Study Eye at Scheduled Visits	Evaluable Set
14.2.3.2	Presence of Intraretinal Fluid as Measured by SD-OCT in the Study Eye at Scheduled Visits	PP Set
14.2.3.3	Summary of Maximum Height of Intraretinal Fluid (microns) and Change from Baseline as Measured by SD-OCT in the Study Eye at Scheduled Visits	Evaluable Set
14.2.3.4	Summary of Maximum Height of Intraretinal Fluid (microns) and Change from Baseline as Measured by SD-OCT in the Study Eye at Scheduled Visits	PP Set
14.2.4.1	Presence of Subretinal Fluid as Measured by SD-OCT in the Study Eye at Scheduled Visits	Evaluable Set
14.2.4.2	Presence of Subretinal Fluid as Measured by SD-OCT in the Study Eye at Scheduled Visits	PP Set

Table Number	Title	Set
14.2.4.3	Summary of Maximum Height of Subretinal Fluid (microns) and Change from Baseline as Measured by SD-OCT in the Study Eye at Scheduled Visits	Evaluable Set
14.2.4.4	Summary of Maximum Height of Subretinal Fluid (microns) and Change from Baseline as Measured by SD-OCT in the Study Eye at Scheduled Visits	PP Set
14.2.5.1	Presence of Pigment Epithelial Detachment as Measured by SD-OCT in the Study Eye at Scheduled Visits	Evaluable Set
14.2.5.2	Presence of Pigment Epithelial Detachment as Measured by SD-OCT in the Study Eye at Scheduled Visits	PP Set
14.2.5.3	Summary of Maximum Height of Pigment Epithelial Detachment (microns) as Measured by SD-OCT in the Study Eye at Scheduled Visits	Evaluable Set
14.2.5.4	Summary of Maximum Height of Pigment Epithelial Detachment (microns) as Measured by SD-OCT in the Study Eye at Scheduled Visits	PP Set
14.2.6.1	Presence of Choroidal Neovascularization as Demonstrated by Fluorescein Angiography in the Study Eye at Scheduled Visits	Evaluable Set
14.2.6.2	Presence of Choroidal Neovascularization as Demonstrated by Fluorescein Angiography in the Study Eye at Scheduled Visits	PP Set
14.2.6.3	Summary of Size of Neovascularization (Number of Disc Areas) and Change from Baseline as Demonstrated by Fluorescein Angiography in the Study Eye at Scheduled Visits	Evaluable Set
14.2.6.4	Summary of Size of Neovascularization (Number of Disc Areas) and Change from Baseline as Demonstrated by Fluorescein Angiography in the Study Eye at Scheduled Visits	PP Set
14.2.7.1	Presence of Leakage from Choroidal Neovascularization as Demonstrated by Fluorescein Angiography in the Study Eye at Scheduled Visits	Evaluable Set
14.2.7.2	Presence of Leakage from Choroidal Neovascularization as Demonstrated by Fluorescein Angiography in the Study Eye at Scheduled Visits	PP Set
14.2.7.3	Summary of Size of Leakage from Choroidal Neovascularization (Number of Disc Areas) and Change from Baseline as Demonstrated by Fluorescein Angiography in the Study Eye at Scheduled Visits	Evaluable Set
14.2.7.4	Summary of Size of Leakage from Choroidal Neovascularization (Number of Disc Areas) and Change from Baseline as Demonstrated by Fluorescein Angiography in the Study Eye at Scheduled Visits	PP Set
Safety Analyses		
14.3.1.1	Overall Summary of Treatment-Emergent Adverse Events	Safety Set
14.3.2.1	Summary of All Ocular Treatment-Emergent Adverse Events by System Organ Class and Preferred Term	Safety Set
14.3.2.2	Summary of All Non-Ocular Treatment-Emergent Adverse Events by System Organ Class and Preferred Term	Safety Set

Table Number	Title	Set
14.3.3.1	Summary of All Ocular Treatment-Emergent Adverse Events Suspected to be Related to Investigational Medicinal Product by System Organ Class and Preferred Term	Safety Set
14.3.3.2	Summary of All Non-Ocular Treatment-Emergent Adverse Events Suspected to be Related to Investigational Medicinal Product by System Organ Class and Preferred Term	Safety Set
14.3.4.1	Summary of All Ocular Serious Treatment-Emergent Adverse Events by System Organ Class and Preferred Term	Safety Set
14.3.4.2	Summary of All Non-Ocular Serious Treatment-Emergent Adverse Events by System Organ Class and Preferred Term	Safety Set
14.3.5	Summary of All Adverse Events of Special Interest by System Organ Class and Preferred Term	Safety Set
14.3.6.1	Summary of All Ocular Treatment-Emergent Adverse Events Leading to Subject Withdrawal by System Organ Class and Preferred Term	Safety Set
14.3.6.2	Summary of All Non-Ocular Treatment-Emergent Adverse Events Leading to Subject Withdrawal by System Organ Class and Preferred Term	Safety Set
14.3.7.1	Summary of Ocular Treatment-Emergent Adverse Events by Maximum Severity, System Organ Class and Preferred Term	Safety Set
14.3.7.2	Summary of Non-Ocular Treatment-Emergent Adverse Events by Maximum Severity, System Organ Class and Preferred Term	Safety Set
14.3.8.1	Summary of Slit Lamp Biomicroscopy	Safety Set
14.3.8.2.1	Shift in Overall Results of Slit Lamp Biomicroscopy	Safety Set
14.3.8.2.2	Shift in Slit Lamp Biomicroscopy Anterior and Vitreous Chamber	Safety Set
14.3.8.2.3	Shift in Slit Lamp Biomicroscopy Hypopyon and Retinal Tear and Detachment	Safety Set
14.3.8.2.4	Shift in Slit Lamp Biomicroscopy Lens Status	Safety Set
14.3.8.2.5	Shift in Slit Lamp Biomicroscopy Lens Opacity for Phakic Eyes	Safety Set
14.3.9	Summary of Intraocular Pressure	Safety Set
14.3.10.1.1	Summary of Clinical Laboratory Values - Biochemistry	Safety Set
14.3.10.1.2	Shift in Clinical Laboratory Values - Biochemistry	Safety Set
14.3.10.2.1	Summary of Clinical Laboratory Values - Coagulation	Safety Set
14.3.10.2.2	Shift in Clinical Laboratory Values - Coagulation	Safety Set
14.3.10.3.1	Summary of Clinical Laboratory Values - Hematology	Safety Set
14.3.10.3.2	Shift in Clinical Laboratory Values - Hematology	Safety Set
14.3.11	Summary of Vital Signs	Safety Set
14.3.12.1	Summary of Electrocardiogram Overall Results	Safety Set
14.3.12.2	Shift in Electrocardiogram Overall Results	Safety Set

25. Listings

Listing Number	Title	Set
16.2.1	Subject Disposition	ITT Set
16.2.2	Protocol Deviations	ITT Set

Listing Number	Title	Set
16.2.3.1	Inclusion and Exclusion Criteria	All Patients
16.2.3.2	Subjects Excluded from Analysis Sets	ITT Set
16.2.3.3	Informed Consent	ITT Set
16.2.4.1	Demographics	ITT Set
16.2.4.2	Ocular Medical History	ITT Set
16.2.4.3	Non-Ocular Medical History	ITT Set
16.2.4.4	Prior and Concomitant Ocular Medications	ITT Set
16.2.4.5	Prior and Concomitant Non-Ocular Medications	ITT Set
16.2.4.6	Prior Anti-VEGF IVT Treatment	ITT Set
16.2.5.1	Study Drug Administration	ITT Set
16.2.6.1	Best Corrected Visual Acuity Scores (ETDRS)	ITT Set
16.2.6.2	Spectral Domain – Optical Coherence Tomography	ITT Set
16.2.6.3	Fundus Photography	ITT Set
16.2.6.4	Fluorescein Angiography	ITT Set
16.2.7.1	All Adverse Events	ITT Set
16.2.7.2	Serious Adverse Events	ITT Set
16.2.7.3	Adverse Events of Special Interest	ITT Set
16.2.7.4	Adverse Events Leading to Subject Withdrawal	ITT Set
16.2.7.5	Deaths	ITT Set
16.2.8.1	Slit-Lamp Biomicroscopy	ITT Set
16.2.8.2	Intraocular Pressure	ITT Set
16.2.8.3	Vital Signs	ITT Set
16.2.8.4	Physical Examination	ITT Set
16.2.8.5	Biochemistry	ITT Set
16.2.8.6	Hematology	ITT Set
16.2.8.7	Coagulation	ITT Set
16.2.8.8	Urine Analysis	ITT Set
16.2.8.9	Serology	ITT Set
16.2.8.10	Electrocardiogram	ITT Set

26. Figures

Figures that will be included in the topline delivery are shown in boldface font.

Figure Number	Title	Set
14.2.1	By-Visit Box Plot Summary of BCVA Letter Score in the Study Eye	Evaluable Set
14.2.2	By-Visit Box Plot Summary of Central Subfield Thickness (μm) in the Study Eye as Measured by SD-OCT	Evaluable Set
14.2.3	By-Visit Box Plot Summary of Macular Volume (mm^3) in the Study Eye as Measured by SD-OCT in the Study Eye	Evaluable Set
14.2.4	By-Visit Box Plot Summary of Maximum Height of Pigment Epithelial Detachment (microns) as Measured by SD-OCT in the Study Eye	Evaluable Set

27. Appendix 1

The following algorithms will be used to impute partial dates.

Assessment Type	Start Date	End Date
Medical History	
If only day is missing then impute day as the first of the month ('01').
 
If missing day and month then impute the first of the year ('01JAN').
	
If only day is missing then impute day as the last day of the month ('31' for months 01, 03, 05, 07, 08, 10, 12; '30' for months 04, 06, 09, 11; '29' for month 02 if a leap year; '28' for month 02 if not a leap year).
 
If missing day and month then impute the last of the year ('31DEC').

Prior and Concomitant Medications	
If only day is missing and the month and year are the same as the date of IMP initiation, then impute day as the day of IMP initiation.
 
If only day is missing and month and year are not the same as the date of IMP initiation, then impute the first day of the month ('01').
 
If missing day and month and the year is the same as the date of IMP initiation, then impute day and month as the day and month of IMP initiation.
 
If missing day and month and the year is not the same as the date of IMP initiation, then impute day and month as the first of the year ('01JAN').
	
If only day is missing then impute day as the last day of the month ('31' for months 01, 03, 05, 07, 08, 10, 12; '30' for months 04, 06, 09, 11; '29' for month 02 if a leap year; '28' for month 02 if not a leap year).
 
If missing day and month then impute the last of the year ('31DEC').

Assessment Type	Start Date	End Date
Adverse Events	
Partial start dates for AEs will not be collected.
 
Completely missing start dates for AEs will be imputed as the first dose date unless the corresponding end date indicates the AE could have start earlier, in which case the missing date will be imputed as 01Jan of the same year as the end date.
	
Partial end dates for AEs will not be collected.
 
Completely missing end dates for AEs will not be imputed.

